There is the prospect of a direct benefit to the subject from participating in the study. This study will help researchers more fully understand responses to procedure-induced noxious stimulation and auditory stimuli measured with diffuse optical imaging in subjects during general anesthesia. The information may provide a novel approach in the rational design of methods/therapies for providing anti-nociception and preventing intraoperative awareness.

8. Privacy Provisions

As the outcome of the study will not impact clinical decisions, this information will not become part of any subject's medical record. Potential subjects will be approached during a regularly scheduled visit. Relevant information will be asked from the participants or obtained from their medical records by trained study staff, ensuring privacy. All potential subjects and their decision to participate will be kept confidential and within the research study staff.

9. Confidentiality Provisions

Subjects will be assured of the confidentiality of their information as mandated by the HIPAA regulations of 4/14/03. The data generated by their participation in this study will be maintained in the database via subject coding to protect their identity. All subject related information will be kept in secured, locked cabinets in the Anesthesia Research office and at the P.A.I.N. Group offices, and on the secure servers. Access to any research related records will be limited to the study group. Boston Children's Hospital is the sole site for enrollment and performance of the study. Research folders will be stored in the Anesthesia Research office in a locked cabinet. NIRS data collected will be stored and analyzed by the P.A.I.N. Group members on this study, either on secure electronic servers or in secure office spaces. Data will be de-identified; any data that is linked to the subject's identity will be kept in a locked cabinet in the P.A.I.N. group office space and in locked cabinets in the Anesthesia Research office.

10. Appendices

- A. TechEn CW 7 System
- B. Preoperative Questionnaire
- C. Postoperative Questionnaire

11. References

Avidan, M. S., L. Zhang, B. A. Burnside, K. J. Finkel, A. C. Searleman, J. A. Selridge, L. Saager, M. S. Turner, S. Rao, M. Bottros, C. Hantler, E. Jacobsohn and A. S. Evers (2008). "Anesthesia awareness and the bispectral index." *N Engl J Med* **358**(11): 1097-1108.

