Title: Assessing the Cortical Response to Noxious and Auditory Stimuli Using Near Infrared Spectroscopy in Subjects under General Anesthesia

NCT: NCT02703090

Date: May 22, 2018

Title: Assessing the Cortical Response to Noxious and Auditory Stimuli Using Near Infrared Spectroscopy in Subjects under General Anesthesia

Research Question: To determine the utility of functional near infrared spectroscopy (fNIRS) in the objective, quantitative assessment of nociception and anti-nociception (analgesia) in patients under general anesthesia. A secondary question is the use of fNIRS to measure actual or intended movement either spontaneously, in response to pain, and/or in response to auditory stimuli during general anesthesia.

Significance: This study is part of an ongoing project to determine the value of fNIRS/DOI as a tool for measurement of nociception and anti-nociception and monitoring depth of anesthesia to prevent awareness and pain in patients under general anesthesia. NIRS/DOI is capable of continuously monitoring and tomographically imaging changes in oxy- and deoxyhemoglobin concentrations as a result of noxious stimulation.

Design: Prospective cohort study.

Subjects: Pediatric and adult subjects 12-30 years of age (ASA physical status I or II) undergoing routine electrophysiology procedures in the cardiac catheterization laboratory at Boston Children's Hospital will be eligible for enrollment. We plan to study and obtain useful data sets in 45 subjects with structurally normal hearts undergoing catheter ablation of arrhythmias under planned general endotracheal anesthesia.

Parents/guardians of eligible children and adults will be approached for enrollment at the pre-catheterization evaluation

Variables: Changes in oxyhemoglobin and deoxyhemoglobin concentrations measured by NIRS. Functional NIRS, also known as diffuse optical imaging (DOI), will be used to measure (1) the hemodynamic activations in the bilateral somatosensory cortices and the prefrontal cortices in response to the noxious stimulation (pain) associated with catheter ablation of arrhythmias, and whether these activations are reduced or eliminated by remifentanil, and (2) the hemodynamic activations in the supplemental motor area to actual or intended movement either spontaneously, in response to pain, and/or in response to auditory stimuli.

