The primary objective of this proposal is to determine the utility of an fNIRS approach in the objective, quantitative assessment of analgesia in a surgical environment. In achieving this goal we would provide anesthesiologists with the ability to better manage patient analgesia and would ultimately reduce the incidence of post-operative sequelae, including chronic neuropathic pain. An objective measure of pain signaling in anesthetized patients would not only promote appropriate analgesia during surgery but would allow the impact of analgesia on postoperative recovery and long-term outcomes to be quantified. By using measures that focus on the specific cortical responses associated with the sensation of pain and the activation of brain networks associated with pain, the successful outcome of this study will give rise to clinical trials that could fundamentally improve how pain is managed during and after surgery, leading to improved patient outcomes and reduced health care costs.

3. Preliminary Studies/Progress Report

We performed a pilot study at BCH (Protocol #10-07-0336) to investigate the feasibility of NIRS to measure cortical signals produced by noxious stimulation in patients under general anesthesia. In this study, we found that catheter ablation (radiofrequency or cryoablation) of arrhythmias produced cortical signals that mirror those seen with noxious stimulation in healthy volunteers and fMRI activations in response to pain. This work is being prepared for submission to a peer-reviewed journal.

Our preliminary results with a continuous-wave (CW) imaging system in healthy adults (work performed at the Massachusetts General Hospital) support our hypothesis that it is possible to measure pain stimuli in the hand sensory area, and to co-register the optical signal with fMRI measurements. We have demonstrated that NIRS, also known as diffuse optical imaging (DOI),

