is capable of continuously monitoring and tomographically imaging changes in oxy-and deoxyhemoglobin concentrations during somatosensory stimulation, such as finger tapping, finger tactile, and electrical median nerve stimulation (Becerra, Harris et al. 2008, Minati, Jones et al. 2009, Nambu, Osu et al. 2009) and multiple applications in children (Wolf and Greisen 2009, Watanabe, Homae et al. 2010). We have also shown with fMRI studies that pain stimulation activates sensory areas. Our group has a great deal of experience performing DOI measurements simultaneously with fMRI, and have demonstrated that the functional signals measured with DOI correlate temporally with fMRI signals (Strangman, Culver et al. 2002).

In our previous work using the same approach we have shown that an acute thermal stimulus using an FDA-approved Peltier thermode produces significant and measurable effects that can be measured in a number of cortical regions in healthy volunteers (Becerra, Harris et al. 2008). We have not completed the work on simultaneous fMRI and DOT measures in healthy subjects and this continues under an approved IRB protocol at MGH, 2007-P-000270, entitled “Assessing the Cortical Response to Painful Stimuli with Diffuse Optical Imaging”.

4. Design and Methods

a. Study Design

General Procedures

We plan to study and obtain useful data sets in 45 subjects (12-30 years of age) scheduled for elective electrophysiology procedures in the cardiac catheterization laboratory and undergoing ablation of arrhythmias under planned general endotracheal anesthesia. As a number of subjects may choose to withdraw from the study following enrollment, and because some subjects will not be able to participate in the study if it is not possible to obtain adequate NIRS signals (as discussed below under Study Procedure: Day of Surgery), we plan to enroll 54 subjects to allow for drop-outs.

- **Pre-Operative Visit**

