The only substantive difference between the study protocol and standard clinical care is the administration of remifentanil. Intravenous opioids are typically not given beyond induction of general anesthesia nor during catheter ablation of the arrhythmia.

e. Definition of Primary and Secondary Outcomes/Endpoints

Primary Outcomes:

The primary outcome is the use of NIRS to measure/detect hemodynamic activations in the bilateral somatosensory cortices and the prefrontal cortices in response to the noxious stimulation

(pain) associated with catheter ablation of arrhythmias, and whether these activations are reduced or eliminated by remifentanil.

Secondary Outcome:

The secondary outcome is the use of NIRS to measure hemodynamic activation in the supplemental motor area to actual or intended movement either spontaneously, in response to pain, and/or in response to auditory stimuli.

f. Data Collection Methods, Assessments and Schedule (what assessments performed, how often)

The study will consist of enrollment and a Preoperative Questionnaire at the pre-catheterization work-up, the study protocol during two days if the patient is discharged the same day of the procedure, or three days if the subject is admitted overnight.

Prior to Preoperative Visit:

- Assessment of eligibility criteria

Pre-Operative Visit:

- Presentation of research study, informed consent/assent (20 minutes)
- Preoperative Questionnaire if patient/parents consent/assent (10 minutes)

Day of Procedure:

1) Before Procedure

- Equipment setup (20 minutes). Test run of brush and audio stimuli (10 minutes).
- BIS sensor applied to patient.

2) During Procedure

- Infusion of NaCL or remifentanil started after induction of anesthesia.
- Audio stimuli (5 seconds each) presented to the patient every half an hour.
- Electronic anesthesia record will capture relevant anesthetic and physiologic data. Study Coordinator and/or Research Nurse will document time and duration of ablations, times of catheter insertion and removal, and assure safety of the patient
- An investigator will operate the NIRS equipment.
- NIRS cap with optodes will be removed from the patient just prior to emergence from anesthesia.
- Average duration of an electrophysiologic study with catheter ablation of arrhythmias is 3 to 4 hours.

3) After Procedure

- Postoperative Questionnaire (10 minutes) will be administered before subject is discharged from the hospital, either on the day of or day following the procedure.

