The NIRS instrument will acquire raw data from each detector at ~40 kHz. The individual signals will then be bandpass filtered. Next, the time series pairs from each detector will be converted from wavelength (absorption) to relative concentrations (of oxy-/deoxy-hemoglobin). This will be done with the modified Beer-Lambert Law and the absorption coefficients of oxy- and deoxy-hemoglobin (HbO and Hb, respectively). (The near-IR wavelengths are chosen because oxy-/deoxy-Hb are the predominant absorbers in the tissue at these wavelengths.) The result will be an oxy-Hb and deoxy-Hb time series associated with each source-detector pair.

For each stimulation run, each smoothed oxy-/deoxy-hemoglobin time series will be examined for periodic amplitude fluctuations. Expected fluctuations include heart rate (~1-3 Hz), breathing and/or “v-waves” (~0.1Hz), as well as any fluctuations induced by the experimental paradigm. If the former sources of noise are substantial, an attempt will be made to filter out these fluctuations (in Fourier space). Any analysis of filtered data will be compared to an analysis of the corresponding non-filtered data. The oxy-hemoglobin portion of the experimentally-induced changes are expected to be 4-9 sec out of phase with the paradigm onsets and offsets (as seen in fMRI work as well as in prior optical recordings).

The data analysis will first be performed on a within-subject basis. Then, the original raw optical time series will be averaged across subjects (for corresponding optode placements only, standardized relative to the EEG 10-20 system).

The biological basis for the signals measured by the optical technique is the same as the basis for fMRI and PET scanning. The regions to be sampled in these pilot studies will be several times larger than single voxels in fMRI scanning. Furthermore, experiments with similar optical instruments indicate that these instruments are at least as sensitive as fMRI. With larger sampling regions (up to a factor of 5 or more), and assuming only comparable sensitivity, the optical imaging should require no more subjects than an fMRI study, and perhaps fewer. Furthermore, optical recording can provide 10-100 times the temporal resolution of fMRI. So, since an optical time series would seem to be at least as good as that coming from an individual voxel (or small collections of voxels) from fMRI data, similar group sizes should be adequate for optical experiments (Boas, Dale et al. 2004).

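### The stated question is the utility of fNIRS for assessing analgesia in patients, but the outcome and analysis address only activation and its reduction by remifentanil among usable recordings, with no yield or per-patient measure.

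*Combined protocol and SAP*

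**What the plan says.** **Question and objective.** The synopsis, under Research Question, states: "To determine the utility of functional near infrared spectroscopy (fNIRS) in the objective, quantitative assessment of nociception and anti-nociception (analgesia) in patients under general anesthesia". Section 2 puts the primary objective in the same terms, to "determine the utility of an fNIRS approach in the objective, quantitative assessment of analgesia in a surgical environment", and adds that success would help anesthesiologists manage analgesia better.

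**Outcome.** Section 4.e: "The primary outcome is the use of NIRS to measure/detect hemodynamic activations in the bilateral somatosensory cortices and the prefrontal cortices" during ablation, and "whether these activations are reduced or eliminated by remifentanil".

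**Analysis.** Section 5.c: "The data analysis will first be performed on a within-subject basis". It continues: "Then, the original raw optical time series will be averaged across subjects", for matching optode positions. No per-patient summary, threshold or decision rule is given for the first step.

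**Subjects without a usable recording.** Under 4.a, randomisation follows consent at the pre-operative visit, and signal quality is tested on the day of surgery. The same section says subjects without adequate signal cannot take part, groups them with withdrawals, and concludes: "we plan to enroll 54 subjects to allow for drop-outs". Section 4.b also makes insufficient light detection through scalp or hair an exclusion criterion.

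**Yield.** Sections 5.d and Statistical Issues in the synopsis use the pilot's 5 usable of 11 enrolled. The synopsis (Subjects) and 4.a plan for useful data in 45 subjects, from the same 54 enrolled. Section 5.f has the investigators review data adequacy after 5 subjects and then after every 10, without a threshold or a reported result.

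**The concern.** Utility for assessing analgesia has at least two parts: how often the method gives a reading, and how well a reading tells one state from another in the patient it came from. The plan measures neither. Arm averages can differ clearly while individual readings overlap, and an average over usable recordings says nothing about those who gave none.

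The missing subjects matter because they are losses after randomisation, and loss through inadequate signal is itself evidence on utility. If the trial reports a clear group difference and describes it in the words of its own research question, readers would take it as support for a monitoring tool when the data support something narrower.

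**Working it through.** **1. Reproduce the plan's figures (5.d).**
- Effect size: 3.764 / 2.135 = 1.763, against a null mean of zero.
- Usable sets: the test, alpha and sidedness are not stated. Assuming a two-sample t test at two-sided 0.05, 8 per group gives 90.6% power, which matches the stated eight.
- Enrolment: 8 / (5/11) = 17.6, so 18 per group, and 3 × 18 = 54.

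All three figures reproduce, so the sizing arithmetic is not at fault on this point. It counts usable sets only, and its mean and SD come from the five usable pilot subjects.

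**2. The yield implied in each place.**

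| Basis | Usable of 54 | Share | Not usable |
|---|---|---|---|
| Pilot rate (5.d): 54 × 5/11 = 24.5 | 24 to 25 | about 45% | about 55% |
| Synopsis (Subjects) and 4.a | 45 | 45/54 = 83% | 9/54 = 17% |

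The exact 95% CI for 5/11 is 17% to 77% usable, or 23% to 83% not usable. If the true rate were 5/11, the chance of 45 or more usable in 54 is about 1 in 100 million (1e-8), and 45 usable sets would need 45 / (5/11) = 99 enrolled. The two plans cannot both hold.

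**3. Question against measurement.**

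| Needed for a statement on utility | Provided by 4.e and 5.c |
|---|---|
| Share of randomised patients with a usable recording | None; losses become drop-outs or exclusions |
| Separation of ablation from no ablation within a patient | A within-subject step with no defined summary |
| Response of the signal to an analgesic | Yes, the randomised remifentanil contrast |
| A criterion for utility | None |

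**4. Precision of the missing measures.**
- Yield, exact 95% CI: 24/54 gives 31% to 59%, and 45/54 gives 71% to 92%. For one arm at 8/18 it is 22% to 69%. These surround assumed counts. They show how precisely yield could be reported, not what it will be.
- Placebo-versus-remifentanil AUC at 8 per arm: the smallest significant observed difference is t(0.975, 14) × √(2/8) = 2.145 × 0.5 = 1.07 SD. Under normality with equal SDs, AUC = Φ(1.07/√2) = 0.78. The Hanley–McNeil SE is √{[A(1−A) + 7(Q₁−A²) + 7(Q₂−A²)]/64}, with Q₁ = A/(2−A) = 0.639 and Q₂ = 2A²/(1+A) = 0.684. That is √(0.914/64) = 0.12, and the 95% CI is about 0.55 to 1.0.
- Within-patient measure, placebo arm: if all 8 of 8 usable patients separated the windows correctly, the exact lower limit would be 0.025^(1/8) = 63%. With 15 of 15 (45/3 per arm) it would be 0.025^(1/15) = 78%.

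**The case against.** The strongest reply is that this is an early mechanistic study. The specific aim in section 1 is to measure activations, which matches the first half of the primary outcome. The second half is a randomised contrast that bears directly on analgesia. The study is described as part of an ongoing project, section 2 expects clinical trials to follow, the low pilot yield is disclosed twice, and nowhere do the documents say that a group difference will be declared proof of utility. All of this stands. It supports a narrower conclusion, but the stated question and primary objective still claim more than that.

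A reader might infer that over half of patients will give no reading. The documents do not establish this. It is 6 of 11 in a pilot (exact 95% CI 23% to 83%), and the synopsis and 4.a plan for a 17% loss. Section 2 also describes features of the chosen instrument meant to improve signal quality, though 5.d makes no use of them.

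Nor can every loss be counted as device failure. No reasons are given for the six pilot losses. Section 4.a includes withdrawals, and 4.c asks only for a high likelihood of ablation, so some subjects may have no ablation to record.

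A reader might also multiply a classification accuracy by the yield to get a share of enrolled patients read correctly. That needs a comparison group with mean zero and equal SD, which the documents do not supply. The product would also change by a factor of 0.833/0.455 = 1.8 according to which yield is used.

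**Conclusion.** The point holds as a mismatch between question and measurement. As written, the trial can show that ablation produces a signal and that remifentanil reduces it, in patients with usable recordings. It cannot show utility for assessing analgesia in patients, because yield is not an outcome and no per-patient measure is defined. It does not follow that the tool lacks utility, or that the group contrast is invalid for its narrower purpose.

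The mismatch rests on the text alone and needs no numerical assumption. Its practical size depends on a yield that the documents leave open, between about 24 to 25 and 45 usable of 54. The change should be made before analysis; it does not require a different trial.

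**What to change.** In 4.e and 5.c:

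1. Report the proportion of all randomised subjects with a usable recording, overall and by arm, with 95% CI. Separate inadequate signal, withdrawal and no ablation performed. Add a descriptive table by hair colour and thickness, which the pre-operative questionnaire already records.
2. Define a per-patient measure and report it with a CI: discrimination of ablation from matched no-ablation windows within placebo-arm patients. NIRS is recorded throughout the procedure (4.a), and ablation times and durations are documented (4.f). Give the placebo-versus-remifentanil AUC as descriptive only. It is too imprecise at about 8 per arm, and it measures separation by drug allocation rather than by pain.
3. Limit the conclusion from the group contrast to proof of mechanism in patients with usable recordings.

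Also reconcile the 45 useful sets in the synopsis and 4.a with the 45% rate in 5.d.

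The cost is plan wording and analysis of data already collected. The intervals will be wide, and the reported picture of the tool may be less favourable.

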Statistical Issues: In our pilot study, we were able to collect useable data from five of the eleven subjects that were enrolled (45%). In the five subjects that produced usable results, the signal of interest had a mean value of -3.764×10^{-7} Moles with a standard deviation of 2.135×10^{-7} Moles. This results in a standardized effect size of 1.763, when using a zero mean for the null case. In order to achieve a 90% power level for this measure, the number of usable data sets is therefore eight. Considering our previous success rate of 45%, approximately 18 subjects will need to be enrolled into each group of the study for a total enrollment of 54 subjects. The data analysis will first be performed on a within-subject basis. Then, the original raw optical time series will be averaged across subjects (for corresponding optode placements only, standardized relative to the EEG 10-20 system).

1. Specific Aims /Objectives

The primary aim is to utilize near-infrared spectroscopy (NIRS) in patients under general anesthesia to measure hemodynamic activations in the bilateral somatosensory cortices and the prefrontal cortices in response to the noxious stimulation (pain) associated with catheter ablation of arrhythmias. Randomization of patients to placebo or one of two opioid doses should allow for discrimination between cortical activation and scalp sympathetic changes in response to pain.

Secondary aims are to utilize NIRS to measure hemodynamic activation in the supplemental motor area to actual or intended movement either spontaneously or in response to pain, and in the auditory cortices in response to auditory stimuli.

This study is part of an ongoing project to determine the value of NIRS as a tool for measurement of pain during general anesthesia and to monitor depth of anesthesia in order to prevent awareness.

2. Background and Significance

Anesthesia is a state of drug-induced unconsciousness with suppression of sensory perception, differing from normal sleep by the intensity of stimulus required to awaken the brain to conscious perception. Anesthesia can be defined by hypnotic (unconsciousness) and analgesic (pain relief) components, so that clinical anesthesia involves the administration of hypnotic and analgesic agents with the anesthesiologist observing the clinical response to noxious stimuli and adjusting the dosage to achieve an adequate depth of anesthesia.

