Near infrared spectroscopy (NIRS) is a spectroscopic method that uses light in the near-infrared region of the electromagnetic spectrum. Near-infrared light (700-1000 nm) penetrates superficial layers (skin, subcutaneous fat, skull, etc.) and is either absorbed by chromophores (oxy- and deoxyhemoglobin) or scattered within the tissue. NIRS is a noninvasive and relatively low-cost optical technique that is becoming a widely used instrument for measuring tissue oxygen saturation, changes in hemoglobin volume and, indirectly, brain blood flow and oxygen consumption (Ferrari, Mottola et al. 2004). NIRS can also be used for non-invasive assessment of brain function through the intact skull by detecting changes in blood hemoglobin concentrations associated with neural activity, and may be considered as a partial replacement for fMRI. It can be used on infants and children, allowing for freely moving subjects since the monitors are applied to the head. Because of limitations of light penetrance, NIRS can only be used to measure brain activity in cortical regions. NIRS has been used to measure the cortical activation in response to tactile, thermal, and painful stimuli (Becerra, Harris et al. 2008, Becerra, Harris et al. 2009, Yucel, Aasted et al. 2015).

The optical imaging system we plan to use for this project is the Continuous Wave (CW) 7 Near-Infrared Spectrometer (TechEn Inc., Milford, MA). The TechEn CW 7 is intended for the continuous noninvasive monitoring of changes in hemoglobin during functional activities (such as touch, pain, thermal sensation, movement). The TechEn CW 7 is principally the same as the TechEn CW 6 but with new features that include smart lasers with software intensity power control, short distance probes, and other techniques to improve ease of use and signal quality (Appendix A). The TechEn CW 6 is currently used only for research applications and includes monitoring tissue oxygenation in brain, breast, and muscle. The TechEn CW 6 device has been

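### Randomization to placebo or remifentanil tests the drug's effect on the total NIRS signal; it does not by itself separate cortical from scalp changes, as Section 1 expects

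*Combined protocol and SAP*

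**What the plan says.** Section 1 (Specific Aims/Objectives) treats scalp sympathetic change as a rival source of the signal and gives randomization as the means of dealing with it: assignment to "placebo or one of two opioid doses should allow for discrimination between cortical activation and scalp sympathetic changes in response to pain".

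The primary outcome in Section 4.e, repeated under Variables in the synopsis, concerns activations in the somatosensory and prefrontal cortices during ablation and asks "whether these activations are reduced or eliminated by remifentanil". Sections 4.a and 4.d define three arms: saline and two remifentanil infusion rates.

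Section 5.c ends its processing with one oxyhemoglobin and one deoxyhemoglobin series per source-detector pair. The steps that might bear on the signal's source are:
- a general filter, without cut-offs: "The individual signals will then be bandpass filtered";
- a conditional Fourier filter for heart-rate, breathing and v-wave fluctuations;
- an expectation that the oxyhemoglobin change is "expected to be 4-9 sec out of phase with the paradigm onsets and offsets".

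Elsewhere, the synopsis credits the technique with "tomographically imaging changes in oxy- and deoxyhemoglobin concentrations as a result of noxious stimulation". Section 2 lists short distance probes among the CW 7's new features and refers to Appendix A, which is not in the text supplied.

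**The concern.** Randomization protects the comparison of arms. It says nothing about which tissue produced the difference. Section 1 describes the scalp change as itself a response to pain, so an analgesic might plausibly reduce both components (an assumption; the document does not say). The arms would separate the two only if remifentanil left one of them alone, or moved each in a known and different way by dose. The plan states neither.

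At stake is the wording of the primary result. With same-sign components, a fall in scalp signal could be reported as reduced cortical activation. With opposite signs, a real cortical reduction could be partly or wholly hidden. A larger sample cures neither, because the problem is identification and not precision.

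**Working it through.** **The plan's own figures (Section 5.d).** Effect size: 3.764/2.135 = 1.763, as stated. The plan gives no alpha; with two-sided 0.05 assumed, a two-sample t-test has power 85.7% at 7 per arm and 90.6% at 8, which matches the stated eight. (A one-sample test against zero, which is how the text reads, would need 6, with power 92.7%.) Enrolment: 8/0.45 = 17.8, so 18 per group and 3 × 18 = 54. These figures reproduce. They do not decide the point and are used only to cost the fix.

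**What the arms identify.** Write each arm's mean signal as cortical part plus scalp part: Y_g = C_g + S_g for g = placebo, lower rate, higher rate. That gives three observed means and six unknowns (rank 3). Take the pilot mean of -3.764 (×10⁻⁷) for placebo and, for illustration, -1.882 and 0 for the two drug arms. Three accounts give the same arm means:
- all cortical: C = (-3.764, -1.882, 0), S = 0;
- all scalp: S = (-3.764, -1.882, 0), C = 0;
- half each: C = S = (-1.882, -0.941, 0).

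**How wide the ambiguity is.** Let r be the fall in total signal and s the scalp share in the placebo state, with each component falling by 0 to 100%. The document gives neither s nor its sign, so the values of s are assumptions.
- Same sign: cortical reduction runs from max(0, (r-s)/(1-s)) to min(1, r/(1-s)).
- Opposite sign (s as a fraction of the net signal): from r/(1+s) to min(1, (r+s)/(1+s)).

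| Fall r | Signs | s = 10% | s = 25% | s = 50% |
|---|---|---|---|---|
| 0% | opposite | 0-9% | 0-20% | 0-33% |
| 25% | same | 17-28% | 0-33% | 0-50% |
| 50% | same | 44-56% | 33-67% | 0-100% |
| 50% | opposite | 45-55% | 40-60% | 33-67% |
| 75% | same | 72-83% | 67-100% | 50-100% |
| 100% | same | 100% | 100% | 100% |
| 100% | opposite | 91-100% | 80-100% | 67-100% |

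The same-sign lower limit reaches zero only when s ≥ r. Scalp suppression alone can therefore account for a fall only if the scalp share is at least as large as the fall.

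**Whether a second dose helps.** Not by itself. With same sign and s = 50%, total falls of 25% and 50% at the two rates fit cortex down 50% and 100% with scalp unchanged, scalp down 50% and 100% with cortex unchanged, or both down 25% and 50%.

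**Whether another step separates them.** The Fourier filter targets periodic noise; a scalp response locked to ablation (an assumption) is not among its targets. The bandpass filter has no stated limits. The expected lag has no scalp timing to be contrasted with. Tomographic imaging is described as a capability, not an analysis step. Section 4.f says "Electronic anesthesia record will capture relevant anesthetic and physiologic data", but 5.c uses none of it. The short distance probes appear in no analysis step.

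**The case against.** The strongest reply is that the arm contrast does not stand alone. Optodes are placed over named regions and standardized to the 10-20 system. Awake finger-tapping and brush runs give a comparison signal. Section 3 reports that pilot ablation signals mirrored fMRI pain activations, and Section 2 says that fNIRS can tell noxious from innocuous stimuli. All this supports a cortical reading as context. None of it is a rule for dividing an arm difference between scalp and cortex, and Section 4.a makes the tapping and brush runs conditional on time.

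It can also be said that the sentence is only an expectation, and that 5.c states no between-arm test, so no formal inference rests on it. That is fair and limits the severity. But 4.e does ask the between-arm question, and this sentence is the only stated means of separation.

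The objection on size stands in part. The 0-100% range and the two-dose example use a 50% share with a 50% fall, which is the boundary case. At a 25% share, a 50% fall requires at least a 33% cortical reduction.

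A reader might infer three stronger things that the document does not support:
- That any reduction could be pure scalp. This fails when the share is smaller than the fall, and for complete same-sign elimination unless the signal was entirely scalp.
- That scalp correction is ruled out. Short distance probes are listed and Appendix A was not supplied, so their use is unspecified.
- That the randomized comparison is invalid. It still tests remifentanil's effect on the measured signal.

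**Conclusion.** The concern holds in a limited form. Section 1 attributes to randomization a property that the design lacks, and 5.c supplies no substitute. Followed as written, the trial can show whether remifentanil changes the NIRS signal over the named regions. It cannot show how much of a partial change is cortical.

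The size depends on a scalp share and sign that the document does not give. A 10% share leaves little doubt (44-56% cortical for a 50% same-sign fall), while a 50% share leaves the source open. Opposite signs allow a hidden cortical reduction of up to 9%, 20% or 33% at shares of 10%, 25% and 50%. They also mean that a net signal of zero need not be zero cortical activity. The identification argument itself rests on no numerical assumption, only on the absence of any stated difference in how the drug acts on the two components. This should be corrected, but it does not undermine the trial's basic comparison.

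**What to change.** **(1) Wording; sufficient by itself.** In Section 1, state that randomization tests remifentanil's effect on the measured NIRS signal and does not by itself separate cortical from scalp components. In the synopsis Variables and in 4.e, report the arm result as a change in NIRS signal over the named regions unless a scalp-correction analysis supports a cortical reading. This costs a text change and no data.

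**(2) Secondary, only if short-distance channels are recorded.** Add to 5.c a sensitivity analysis giving the ablation response by arm with and without short-channel correction, and the short-channel response by arm. Prespecify one dose contrast, one chromophore and one region; the rest are descriptive. A corrected difference whose confidence interval excludes zero supports a cortical origin but does not prove it, since scalp signal may remain after correction. Otherwise, report the source as unresolved.

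**Cost of (2).** Correction adds noise and may remove true signal. Suppose that it keeps a fraction f of the pilot mean, the SD rises by 20%, and remifentanil abolishes the signal (all assumed; two-sample t, two-sided 0.05). Then d = 1.763 × f/1.2:

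| f | d | Power, 8 per arm | Power, 15 per arm |
|---|---|---|---|
| 100% | 1.469 | 78% | 97% |
| 75% | 1.102 | 54% | 83% |
| 50% | 0.735 | 28% | 49% |

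Eight per arm follows from the 45% usable rate (0.45 × 18 = 8.1). Fifteen follows from the 45 planned useful data sets split equally (45/3). A partial drug effect would lower power further: halving the signal with f = 100% gives the same d as the last row. This is why (2) should stay secondary.
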